## 11. REPORTING ADVERSE EVENTS

DEFINITION: AE means any untoward medical occurrence associated with the use of a drug in humans, whether or not considered drug related. An AE can therefore be any unfavorable and unintended sign), symptom, or disease temporally associated with participation in a study, whether or not related to that participation. This includes all deaths that occur while a participant is on a study.

Please note that all abnormal clinical laboratory values that are determined to be of clinical significance based on a physician's assessment are to be reported as AEs. Those labs determined to be of no clinical significance or of unknown clinical significance (per the physician's assessment) should not be reported as AEs. Any lab value of unknown clinical significance should continue to be investigated/followed-up further for a final determination, if possible.

A list of AEs that have occurred or might occur can be found in §6.2 Reported Adverse Events and Potential Risks, as well as the Investigator Brochure or package insert.

### 11.1 Adverse Events

#### 11.1.1 Reportable AEs

All AEs that occur after the informed consent is signed and baseline assessments are completed (including run-in) must be recorded on the AE CRF (paper and/or electronic) whether or not related to study agent.

#### 11.1.2 AE Data Elements:

The following data elements are required for AE reporting.

- AE verbatim term
- NCI Common Terminology Criteria for Adverse Events version 4.0 (CTCAE v4.0) AE term (MedDRA lowest level term)
- CTCAE (MedDRA) System Organ Class (SOC)
- Event onset date and event ended date
- Treatment assignment code (TAC) at time of AE onset
- Severity grade
- Attribution to study agent (relatedness)
- Whether or not the event was reported as a SAE
- Whether or not the participant dropped out due to the event
- Outcome of the event

#### 11.1.3 Severity of AEs

11.1.3.1 Identify the AE using the CTCAE version 4.0. The CTCAE provides descriptive terminology (MedDRA lowest level term) and a grading scale for each AE listed. A copy of the CTCAE can be found at [http://ctep.cancer.gov/protocolDevelopment/electronic\\_applications/ctc.htm](http://ctep.cancer.gov/protocolDevelopment/electronic_applications/ctc.htm)

AEs will be assessed according to the grade associated with the CTCAE term. AEs that do not have a corresponding CTCAE term will be assessed according to the general guidelines for grading used in the CTCAE v4.0. as stated below.

**CTCAE v4.0 general severity guidelines:**

Grade	Severity	Description
1	Mild	Mild; asymptomatic or mild symptoms; clinical or diagnostic observations only; intervention not indicated.
2	Moderate	Moderate; minimal, local or noninvasive intervention indicated; limiting age-appropriate instrumental activities of daily living (ADL)*.
3	Severe	Severe or medically significant but not immediately life-threatening; hospitalization or prolongation of hospitalization indicated; disabling; limiting self-care ADL**.
4	Life-threatening	Life-threatening consequences; urgent intervention indicated.
5	Fatal	Death related to AE.

**ADL**

\*Instrumental ADL refers to preparing meals, shopping for groceries or clothes, using the telephone, managing money, *etc.*

\*\*Self-care ADL refers to bathing, dressing and undressing, feeding self, using the toilet, taking medications, and not bedridden.

11.1.4 Assessment of relationship of AE to treatment

The possibility that the AE is related to study agent will be classified as one of the following: not related, unlikely, possible, probable, definite.

11.1.5 Follow-up of AEs

All AEs, including lab abnormalities that in the opinion of the investigator are clinically significant, will be followed according to good medical practices and documented as such.

**11.2 Serious Adverse Events**

11.2.1 DEFINITION: Regulations at 21 CFR §312.32 (revised April 1, 2014) defines an SAE as any untoward medical occurrence that at any dose has one or more of the following outcomes:

- Death
- A life-threatening AE
- Inpatient hospitalization or prolongation of existing hospitalization
- A persistent or significant incapacity or substantial disruption of the ability to perform normal life functions
- A congenital anomaly or birth defect

- Important medical events that may not be immediately life-threatening or result in death or hospitalization should also be considered serious when, based upon appropriate medical judgment, they may jeopardize the participant and may require intervention to prevent one of the other outcomes.

## 11.2.2 Reporting SAEs

The organization that experiences the serious adverse event (SAE) should report the SAE to the following four (4) entities: 1) NCI DCP; 2) DCP's regulatory contractor CCSA; 3) MDACC, the CLO; and 4) BHR Pharma, LLC. Detailed reporting instructions are provided below. In addition, all participating organizations will follow Central IRB (CIRB) and their local IRB requirements for SAE reporting.

11.2.2.1 The Lead Organization and all Participating Organizations will report SAEs on the DCP SAE Report Form found at <https://prevention.cancer.gov/clinical-trials/clinical-trials-management/protocol-information-office/pio-instructions-and-tools/2012-consortia>.

11.2.2.2 Contact the DCP Medical Monitor by phone within 24 hours of knowledge of the event.

[name]  
Division of Cancer Prevention  
National Cancer Institute  
[name]  
[name]  
Office [contact]  
Cell [name]  
[contact]  
Email: [contact]

Include the following information when calling the Medical Monitor:

- Date and time of the SAE
- Date and time of the SAE report
- Name of reporter
- Call back phone number
- Affiliation/Institution conducting the study
- DCP protocol number
- Title of protocol
- Description of the SAE, including attribution to drug

11.2.2.3 Contact the Consortium Lead Organization (CLO) PI, [name], or designee by phone, fax or email listed on the protocol face page within 24 hours of knowledge of the event. The same information reported to the DCP Medical Monitor should be provided to the CLO PI or designee via email, phone or fax within 24 hours of knowledge of the event.

11.2.2.4 The Lead Organization and all Participating Organizations will email written SAE reports to DCP's Regulatory Contractor CCS Associates, Inc. (CCSA; [contact]) at [[contact]](mailto:[contact]) within 48 hours of learning of the event using the fillable SAE Report Form.

11.2.2.5 The CLO PI, [name], or designee must be copied on the email sent to DCP's Regulatory Contractor CCS Associates, Inc.

11.2.2.6 BHR Pharma, LLC and Besins Pharmacovigilance ([[contact]](mailto:[contact])) must be copied on the email sent to DCP's Regulatory Contractor CCS Associates, Inc.

11.2.2.7 The DCP Medical Monitor and CCSA regulatory and safety staff will make an initial assessment of the SAE and communicate with BHR Pharma, LLC who will determine which SAEs require FDA submission as IND safety reports.

11.2.2.8 BHR Pharma, LLC will provide a standard report for the Lead Organization and all Participating Organizations to comply with applicable regulatory requirements related to reporting SAEs to the CIRB/IRB/IEC.

### 11.2.3 Follow-up of SAE

Site staff should send follow-up reports as requested when additional information is available. Additional information should be entered on the DCP SAE Report Form in the appropriate format. Follow-up information should be sent to DCP as soon as available, with a copy to BHR Pharma, LLC and Besins Pharmacovigilance ([[contact]](mailto:[contact])). SAEs related to the study agent will be followed until resolved.

## 12. STUDY MONITORING

### 12.1 Data Management

This study will report clinical data using the Data Management Initiative (DMI) web-based application managed by the Consortium Biostatistics and Data Management Core. Data Management Initiative (DMI) infrastructure has been developed in the Division of Quantitative Sciences (DQS), MD Anderson Cancer Center. This infrastructure supplies integrated database and software services for web-based data collection, randomized treatment assignment, reporting, query, data download, and data quality management. The DMI will be the database of record for the protocol and subject to NCI and FDA audit. All DMI users will be trained to use the DMI system and will comply with the instructions in the protocol-specific "DMI User Manual" as well as applicable regulatory requirements such as 21 CFR; Part 11. Data management procedures for this protocol will adhere to the Data Management Plan (DMP) on file at the DCP for contract HHSN261201200034I.

### 12.2 Case Report Forms

Participant data will be collected using protocol-specific CRF developed from the standard set of DCP Chemoprevention CRF Templates and utilizing NCI-approved Common Data Elements (CDEs). The approved CRFs will be used to create the electronic CRF (e-CRF) screens in the DMI application. Site staff will enter data into the e-CRFs in DMI. CRF amendments, if needed, will be submitted to the DCP Protocol Information Office for review and approval prior to deployment in DMI. Approved changes will be programmed into the DMI database by the Consortium Biostatistics and Data Management Core.

### 12.3 Source Documents

Source documentation will include only those documents containing original forms of data, including clinic charts, shadow files, hospital charts, and physician notes. Data recorded directly on the CRFs designated

as source documents (i.e., no prior written or electronic record of data) will be considered source data. All other data recorded on the CRFs will not be considered source documentation.

## 12.4 Data and Safety Monitoring Plan

The Data and Safety Monitoring Plan for the MD Anderson Consortium is on file at the DCP. This study will be monitored yearly by the MDACC Data and Safety Monitoring Board (DSMB), the data and safety monitoring board of record for this study. The DSMB reports to the President, or his designee, as the on-campus representative of The University of Texas Board of Regents. It oversees the data and patient safety issues for randomized clinical trials that originate at MD Anderson; that are coordinated or analyzed by MD Anderson and are not being monitored by any other DSMB; or have been designated as requiring DSMB monitoring at the request of the IRB, the CRC, or institution. The primary objectives of the DSMB are to ensure that patients' rights pertaining to participation in a research study are protected, and that patients' interests are prioritized over the interests of the scientific investigation. Responsibilities include:

- (a) Review interim analyses of outcome data (prepared by the study statistician or other responsible person at the time points defined in the study) approved by the IRB and additional time points as determined by the DSMB, and to recommend, if necessary, whether the study needs to be changed or terminated based on these analyses;
- (b) Determine whether, and to whom, outcome results should be released prior to the reporting of study results;
- (c) Review interim toxicity data and efficacy of treatment;
- (d) Review major research modifications proposed by the investigator or appropriate study committee prior to implementation (e.g., termination, dropping an arm based on toxicity results from the study or results of other studies, increasing target sample size).

Refer to the Data and Safety Monitoring Plan for the MD Anderson Consortium on file at the DCP for further details.

## 12.5 Sponsor or FDA Monitoring

The NCI, DCP (or their designee), pharmaceutical collaborator (or their designee), or FDA may monitor/audit various aspects of the study. These monitors will be given access to facilities, databases, supplies and records to review and verify data pertinent to the study.

## 12.6 Record Retention

Clinical records for all participants, including CRFs, all source documentation (containing evidence to study eligibility, history and physical findings, laboratory data, results of consultations, *etc.*), as well as IRB records and other regulatory documentation will be retained by the Investigator in a secure storage facility in compliance with Health Insurance Portability and Accountability Act (HIPAA), Office of Human Research Protections (OHRP), Food and Drug Administration (FDA) regulations and guidances, and NCI/DCP requirements, unless the standard at the site is more stringent. The records for all studies performed under an IND will be maintained, at a minimum, for two years after the approval of a New Drug Application (NDA). For NCI/DCP, records will be retained for at least three years after the completion of the research. NCI will be notified prior to the planned destruction of any materials. The records should be accessible for inspection and copying by authorized persons of the Food and Drug Administration. If the

study is done outside of the United States, applicable regulatory requirements for the specific country participating in the study also apply.

## **12.7 Cooperative Research and Development Agreement (CRADA)/Clinical Trials Agreement (CTA)**

The agent(s) supplied by DCP, NCI, used in this protocol, is/are provided to the NCI under a Collaborative Agreement (CRADA, CTA) between the Pharmaceutical Company(ies) (hereinafter referred to as Collaborator(s)) and the NCI Division of Cancer Prevention. Therefore, the following obligations/guidelines, in addition to the provisions in the “Intellectual Property Option to Collaborator” contained within the terms of award, apply to the use of Agent(s) in this study:

12.7.1 Agent(s) may not be used for any purpose outside the scope of this protocol, nor can Agent(s) be transferred or licensed to any party not participating in the clinical study. Collaborator(s) data for Agent(s) are confidential and proprietary to Collaborator(s) and shall be maintained as such by the investigators. The protocol documents for studies utilizing investigational agents contain confidential information and should not be shared or distributed without the permission of the NCI. If a participant taking part in the study or participant’s family member requests a copy of this protocol, the individual should sign a confidentiality agreement. A suitable model agreement can be downloaded from the DCP website.

12.7.2 For a clinical protocol where there is an Investigational Agent used in combination with (an) other investigational Agent(s), each the subject of different collaborative agreements, the access to and use of data by each Collaborator shall be as follows (data pertaining to such combination use shall hereinafter be referred to as "Multi-party Data").

12.7.3 NCI must provide all Collaborators with prior written notice regarding the existence and nature of any agreements governing their collaboration with NIH, the design of the proposed combination protocol, and the existence of any obligations that would tend to restrict NCI's participation in the proposed combination protocol.

12.7.4 Each Collaborator shall agree to permit use of the Multi-Party Data from the clinical trial by any other Collaborator solely to the extent necessary to allow said other Collaborator to develop, obtain regulatory approval, or commercialize its own investigational agent.

12.7.5 Any Collaborator having the right to use the Multi-Party Data from these trials must agree in writing prior to the commencement of the trials that it will use the Multi-Party Data solely for development, regulatory approval, and commercialization of its own investigational agent.

12.7.6 Clinical Trial Data and Results and Raw Data developed under a collaborative agreement will be made available exclusively to Collaborator(s), the NCI, and the FDA, as appropriate. All data made available will comply with HIPAA regulations.

12.7.7 When a Collaborator wishes to initiate a data request, the request should first be sent to the NCI, who will then notify the appropriate investigators of Collaborator's wish to contact them.

12.7.8 Any manuscripts reporting the results of this clinical trial must be provided to DCP for immediate delivery to Collaborator(s) for advisory review and comment prior to submission for publication. Collaborator(s) will have 30 days (or as specified in the CTA) from the date of receipt for review. Collaborator shall have the right to request that publication be delayed for up to an additional 30 days in

order to ensure that Collaborator's confidential and proprietary data, in addition to Collaborator(s)'s intellectual property rights, are protected. Copies of abstracts must be provided to DCP for forwarding to Collaborator(s) for courtesy review as soon as possible and preferably at least three days prior to submission, but in any case, prior to presentation at the meeting or publication in the proceedings. Press releases and other media presentations must also be forwarded to DCP prior to release. Copies of any manuscript, abstract, and/or press release/ media presentation should be sent to the Protocol Information Office at [NCI\\_DCP\\[contact]](mailto:[contact]).

The Protocol Information Office will forward manuscripts to the DCP Project Officer for distribution to the Collaborator(s). No publication, manuscript or other form of public disclosure shall contain any of Collaborator's confidential/proprietary information.

### **13. STATISTICAL CONSIDERATIONS**

Note: Mammogram, blood, and tissue samples for participants seen under COVID-19 contingency plan will have a range of Month 13-18. Laboratory tests and research bloods not collected at Month 6 under the COVID-19 contingency plan, will result in missing data.

#### **13.1 Study Design/Description**

A total of 198 potentially eligible participants will be consented and screened for eligibility and, with a conservative estimate, 158 (80%) participants are expected to be eligible. These 158 women will be randomized 1:1 into one of two groups: placebo or 4-OHT gel 2 mg per breast. Treatment will last for 52 weeks. Considering an attrition rate of approximately 19%, we expect to have 128 evaluable women who will have both baseline and 52-week measurements of percent MD of the breast, 64 women in each group.

With 64 women in each group, we will have an 80% power to detect a decrease of percent MD of 6% in treatment group against 2% in placebo group, with a common standard deviation of 8%, using a two-sided t-test with a significance level of 0.05. The proposed difference between the active treatment and placebo groups and the standard deviation are based on conservative estimates from the published work by Cuzick et al. The sample size calculation is performed using nQuery + nTerim 3.0.

#### **13.2 Randomization/Stratification**

Participants will be assigned a randomization number once the following has been accomplished: eligibility has been verified at the site level, eligibility has been confirmed by the site PI, and eligibility CRF has been entered into the DMI web application. The randomization number will be generated by the database and assigned to the participant.

A total of 158 women will be enrolled and randomized 1:1 into one of two groups. Treatment will last for 52 weeks. Considering an attrition rate of approximately 19%, we expect to have 128 evaluable women who will have both baseline and 52-week measurements of percent MD of the breast, 64 women in each group.

We will stratify the randomization by study site (UT MD Anderson Cancer Center, Dana Farber Cancer Institute, Northwestern University, Moffitt Cancer Center, University of Arizona Cancer Center, University of Minnesota, and University of Wisconsin) and baseline breast density category (heterogeneously dense (C), extremely dense (D)) using random permuted block design with the block size of 4.

### 13.3 Accrual and Feasibility

We plan to consent and screen 198 potential participants over 25 to 30 months at seven clinical centers. Our goal is to randomize 158 eligible participants. The randomized participants will receive the intervention for 52 weeks. They will be followed closely to monitor the toxicity and drug compliance.

### 13.4 Primary Objective, Endpoint(s), Analysis Plan

The primary objective of this study is to evaluate the change in percent MD (using Cumulus software) from baseline to the week 52 in women applying 4 mg OHT gel versus placebo based on the intent-to-treat principle. The intent-to-treat population is defined as all participants who are randomized and have MD measurements from both baseline and 52 weeks. The primary analysis will be performed comparing the active group versus placebo group per randomization, regardless of the compliance of each participant.

The percent MD is the MD (percent dense area) that is visually estimated using both the mediolateral oblique (MLO) view and the craniocaudal (CC) view as the proportion of the total breast area that was composed of dense tissue (to the nearest 5%). For the study purpose, the densest breast will be the target lesion for the primary endpoint. Breast biopsy for secondary and exploratory endpoints will be performed in the opposite (non-target) breast.

At the end of the study, all participants who have MD measurements from both baseline and 52 weeks, regardless of the compliance, will be included in the primary analysis. Change in percent MD of the breast from baseline to 52 weeks will be summarized using descriptive statistics, such as mean, standard deviation, median and range for each arm. With visual assessments of MD from both the MLO and CC views for evaluating the primary endpoint, Hotelling's  $T^2$  test will be used to conduct multivariate hypothesis testing which includes both views. Hotelling's  $T^2$  test represents the multivariate generalization to the independent two-sample t-test in the univariate setting. The correlation and variance-covariance matrix will be assessed to estimate the level of dependency between the MLO and the CC views. The mean change in percent MD at 52 weeks incorporating both the MLO and CC views will be compared between the two groups utilizing Hotelling's  $T^2$  test. Q-Q plots, used to visually assess the assumption of normality, will be constructed for the marginal distributions associated with observations emanating from both the MLO and the CC view. Assuming the mean difference in density between the observations between the 4-OHT and the placebo groups is approximately normally distributed, then the primary analysis will be conducted as previously described. Additionally, a 95% confidence ellipse (simultaneous confidence intervals) for the mean vector containing information from both views will be provided. If the change in density is not normally distributed, then we will try to rescale to achieve approximate normality by using the Box-Cox transformation. In our prior experience evaluating change in density in response to oral tamoxifen, change in density was scaled and raised to the 1.75th power to approximate normality. We will have to determine what power to use in the Box-Cox transformation based on the data that we have on hand. Transformations may be performed when necessary to make the measure of MD close to normal distribution before evaluating the change of MD over time between two groups. If the Hotelling's  $T^2$  test is significant, we will further examine whether the significant difference between the 4-OHT gel group and the placebo group is in the MLO view or the CC view or both. Note that the sample size calculation is based on the two-sample t-test. It provides a conservative estimate of the statistical power because the Hotelling's  $T^2$  test is more efficient than the two-sample t-test.

We will evaluate if the change of breast density is different in patients with heterogeneously dense (C) vs extremely dense (D) breast at baseline, by incorporating this covariate and its interaction with treatment over time in the repeated measures analysis.

Due to the COVID-19 closures of clinical research activities, a small number of participants (less than 20) will have their month 12 visits by telephone. These participants will continue the randomized treatments and have mammograms in the month 13-18 visits. The measurements of breast density from the month 13-18 (instead of month 12) visits will be used as the primary endpoint. We will first provide summary statistics for the breast density from the month 13-18 visits, from the month 12 visit, and then graphically explore any impact of potentially longer exposures of the treatment on the primary endpoint of mammographic breast density. If appropriate, we will incorporate the timing of the measurement as a covariate in the analysis to estimate the effect of prolonged exposure of the treatment on mammographic breast density. We will also perform a sensitivity analysis by including month 13-18 measures as primary endpoint, and by excluding month 13-18 measures to evaluate the impact of the different timing of measurements on the primary endpoint analysis. For the sample size calculation, we have factored in a 19% inevaluable rate. Based on the current estimate, even including the follow-up delayed caused by COVID-19, the inevaluable rate is still within 19%. Note that patients who were randomized but never started treatments will be replaced if the inevaluable rate is above 19%.

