APPENDIX H: Resources for tobacco and alcohol quitting

APPENDIX I: Specimen Inventory Form

## 1. OBJECTIVES

The overall objective is to evaluate whether daily application of 2mg (2mL) per breast of 4-hydroxytamoxifen (4-OHT) topical gel versus placebo lowers breast density in women with mammographically dense breast, based on the intent-to-treat principle, i.e., all participants who have MD measurements from both baseline and 52 weeks, regardless of compliance, will be included in the primary analysis.

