### **13.6 Reporting and Exclusions**

Every reasonable attempt will be made to recover any missing data. If any data for the primary efficacy measure remains missing, then the change of the primary endpoint will not be calculated, and the participant will not be evaluable for the primary endpoint. We will also consider multiple imputations using predictive values based on regression models under the assumption of missing at random to supplement the primary analysis. In addition, any available data will be included in the repeated measure analysis for both primary and secondary endpoints, which allows for all participants with complete or partial data.

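### The set named intent-to-treat is a complete-case set that may omit about 30 of 158 women; Section 13.8 describes a different main population, and no planned analysis varies the missing-at-random assumption

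*Combined protocol and SAP*

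**What the plan says.** **Population.** Section 13.4: "The intent-to-treat population is defined as all participants who are randomized and have MD measurements from both baseline and 52 weeks". Section 1 explains the intent-to-treat principle the same way: "all participants who have MD measurements from both baseline and 52 weeks, regardless of compliance, will be included in the primary analysis". Comparison is by assigned arm whatever the adherence. For a woman with missing primary data, Section 13.6 says "the change of the primary endpoint will not be calculated, and the participant will not be evaluable for the primary endpoint".

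**Expected losses.** Sections 13.1 and 13.2 randomize 158 and expect 128 evaluable, 64 per arm, after about 19% attrition. Section 13.4 adds that "even including the follow-up delayed caused by COVID-19, the inevaluable rate is still within 19" percent, and that "patients who were randomized but never started treatments will be replaced if the inevaluable rate is above 19" percent. Section 8.4, by contrast, allows for 7 extra women per arm.

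**Other description of the main population.** Section 13.8 puts women who met the entry criteria into the main analysis, possibly leaving out those given no gel, and rests every efficacy conclusion on the eligible women. Its opening sentence also wants response assessed in women found ineligible. None of this requires two images.

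**Study status.** Section 6.9 has the site investigator take a woman off study when her blind is broken early. The listed reasons include toxicity thought to be drug-related, and pregnancy. Section 8.4 keeps women who stop the gel in the study where feasible so that routine mammograms can be collected. Sections 7.3 and 7.4 tie off-study status in pregnancy to its known outcome.

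**Missing data.** Section 13.6 promises recovery efforts ("Every reasonable attempt will be made to recover any missing data"), commits to a repeated-measures analysis of complete and partial data, and adds: "We will also consider multiple imputations using predictive values based on regression models under the assumption of missing at random". Section 13.5 also plans a linear mixed model for density over time.

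**The concern.** Intent-to-treat normally means everyone randomized, analysed as randomized. Here membership depends on having a 52-week image, which is known only after treatment has begun. Ignoring adherence deals with women who stop the gel but are imaged; it does nothing for women with no follow-up image. A result reported under this label would apply to women with both images only.

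If the lost women would have changed differently from those retained, and this differs by arm, the complete-case difference is not the difference among all randomized women. Unblinding for toxicity thought to be drug-related, followed by removal from the study, is one route by which losses could depend on arm.

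The two population descriptions also leave two analysts free to build different primary data sets: are untreated women in, are ineligible women in, and do replaced women stay in? Finally, every planned handling of missing data makes the same assumption, so a reader could not tell whether the conclusion depends on it.

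**Working it through.** **Inputs from the documents (13.1, 13.2).** 158 randomized 1:1 (79 per arm); 64 evaluable per arm; mean decreases of 6 and 2 points; SD 8; two-sided 0.05; t-test.

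**The plan's own figures.** Standardized difference 4/8 = 0.5. The two-sample t-test needs 63.8, so 64 per arm; power at 64 is 80.1%. Also 128/0.81 = 158.02. Both stated figures reproduce. Women outside the analysis set: 158 − 128 = 30, and 30/158 = 19.0%. Per arm: 79 − 64 = 15, against the 7 in Section 8.4.

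**Assumptions.** The documents give no losses by arm and no outcomes in lost women. I take 15 of 79 lost in each arm, and completers at the planned 6 and 2. Let a and p be the mean decrease in lost active and lost placebo women.

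All-randomized difference = (64×6 + 15a)/79 − (64×2 + 15p)/79.

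- a = 6, p = 2 (losses uninformative): 4.00
- a = 2, p = 2 (lost active women have no benefit over placebo): 3.24
- a = 0, p = 2: 2.86
- a = 4, p = 0 (same shortfall in both arms): 4.00
- a = 6, p = 0: 4.38

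Unequal losses matter even when the shortfall is the same. With lost women 4 points worse in both arms, 20 active and 10 placebo lost give (59×6 + 20×2)/79 − (69×2 − 10×2)/79 = 3.49. The reverse split gives 4.51.

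**Tipping point, t-test.** Standard error = 8×√(2/64) = 1.414. The smallest significant difference is 1.979 × 1.414 = 2.80. Shift needed in lost active women: (4 − 2.80)/(15/79) = 6.3 points. With splits of 20/10 or 25/5 (active/placebo) and the standard error for those numbers, it is 4.7 or 3.7 points.

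**Tipping point, planned test.** The primary test is Hotelling's T² on the MLO and CC views, although "Note that the sample size calculation is based on the two-sample t-test". Assume equal differences d in both views, SD 8 per view, 64 per arm and inter-view correlation ρ, which the documents do not give. Then T² = d²/(1 + ρ). The critical value is (2×126/125) × F(0.95; 2, 125) = 2.016 × 3.069 ≈ 6.186 (computed before rounding), so the critical d is √(6.186(1 + ρ)).

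| ρ | critical d | shift in lost active women, 15 of 79 |
|---|---|---|
| 0 | 2.49 | 8.0 |
| 0.5 | 3.05 | 5.0 |
| 0.9 | 3.43 | 3.0 |

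Both 15-of-79 calculations hold the standard error at its value for 64 per arm, and all tipping points assume an observed difference equal to the planned 4 points.

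**The missing-data provisions side by side.** Multiple imputation is optional and assumes missing at random in its own words. The repeated-measures analysis is definite, but if likelihood-based it assumes the same implicitly, and a woman with only a baseline image adds little about change. The stated sensitivity analyses in 13.4 and 13.5 concern visit timing, menopausal transition and hormone therapy. None varies the missing-data assumption.

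**The case against.** The plan is open about its restriction: each definition states the two-measurement condition, so renaming the set changes no number. Under 13.4 a never-started woman with both images is included. Women who stop the gel are still to be imaged, the mammograms are standard of care, and the inevaluable rate is reported as within the allowance. Breaking the blind normally requires consultation with the Medical Monitor, so 6.9 probably affects few women. This is a phase II study meant to inform a larger one.

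The numbers are also fairly reassuring. A shift of 6.3 points puts lost active women at 6 − 6.3 = −0.3, worse than placebo completers. Total loss of benefit leaves 3.24, above the thresholds of 2.80 (t-test), 2.49 and 3.05 (Hotelling, ρ of 0 and 0.5). Only at ρ = 0.9 (3.43) does it fall short.

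All of that stands, and it limits the point. A reader might infer that the plan ignores women with missing images; it does not, since 13.6 commits to an analysis using partial data and only the imputation is optional. Three things remain: the label, the conflicts with 13.8 and 6.9, and the absence of any analysis that varies the missing-at-random assumption.

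**Conclusion.** The point holds as a matter of definition, consistency and untested assumption. About 30 of 158 women (19%) may fall outside a set called intent-to-treat; 19% is a planning allowance, not an observed or capped rate. Sections 13.4 and 13.8 do not describe the same main population. Section 6.9 conflicts with 8.4 and, for pregnancy, with 7.3 and 7.4.

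In the equal-loss illustrations the all-randomized difference runs from 2.86 to 4.38 around a complete-case 4.00. How easily significance would be lost depends on the split of losses and on the inter-view correlation, neither of which the documents give.

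Two stronger readings are not supported. The documents do not show that the primary result is or will be biased: they report no losses by arm and no outcomes in lost women, and the direction could be either. Nor is the trial underpowered on this account: 80% at 64 evaluable per arm is correct as stated. The change is worth making because it is cheap and the result will inform a larger trial.

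**What to change.** 1. **Sections 1 and 13.4.** Rename the present set evaluable (complete-case). Reserve intent-to-treat for all randomized women as randomized, including never-started women who are replaced. Name the repeated-measures analysis already planned in 13.6 as the all-randomized supportive analysis.
2. **Section 13.8.** Align the main population and the basis for efficacy conclusions with 13.4, saying explicitly how ineligible and untreated women are handled.
3. **Section 6.9.** Reconcile study status with 8.4 and with the pregnancy text in 7.3 and 7.4. State that images from a routine Month 12 (or Month 13-18) mammogram, where one is done, are still collected after the blind is broken unless consent is withdrawn. The rules for stopping treatment and for unblinding are unchanged.
4. **Section 13.6.** Add a supplementary two-way tipping-point analysis, shifting lost women in both arms and using the planned test, with placebo-based imputation as one reference case. Describe it as showing sensitivity; it cannot detect bias.
5. **Separately,** reconcile the 7 per arm in 8.4 with the 15 per arm implied by 13.1.

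**Cost.** Amendment wording with DCP and CIRB approval (14.3), possibly consent wording for images collected after off-study status (14.4), and a little more analysis. No visits or procedures are added. The reported result may look less certain than the complete-case one.
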